Study Title: A Randomized, Double-blind, Placebo-controlled, Phase 2 Study to Evaluate the Safety and Efficacy of IW-1973 in Patients with Type 2 Diabetes with Albuminuria Treated with Renin-Angiotensin System Inhibitors
Study Number: C1973-203
Study Phase: 2
Study Objectives Primary 
• To assess the safety and tolerability of oral IW-1973 when administered daily for approximately 12 weeks to adult patients with type 2 diabetes mellitus with albuminuria who are on a stable regimen of renin-angiotensin system inhibitors• To evaluate the effect of oral IW-1973 on renal function when administered daily for approximately 12 weeks to adult patients with type 2 diabetes mellitus with albuminuria who are on a stable regimen of renin-angiotensin system inhibitors
Study Design This multicenter, randomized, double-blind, placebo-controlled, parallel-group study will evaluate 2 dose levels of IW-1973 compared with placebo.
Study Population and Planned Number of Patients The study population will consist of adult patients with type 2 diabetes mellitus, albuminuria, and impaired renal function. Patients must have been taking antihyperglycemic medications for at least 12 weeks and with their regimen stable (ie, drug and dose) for at least 28 days before the Randomization Visit. Additionally, patients must have been on a stable regimen of an angiotensin-converting enzyme inhibitor (ACEi) or an angiotensin receptor blocker (ARB), for at least 28 days before the Randomization Visit. For details, see Eligibility Criteria . Approximately 150 patients (50 per arm) will be stratified by baseline estimated glomerular filtration rate (eGFR) (ie, eGFR 30 to 45, >45 to 60, and >60 to 75 mL/min/1.73 m ²) and randomized 1:1:1 to daily 20 mg IW-1973, 40 mg IW-1973, or placebo. Patients who withdraw from the study after Randomization will not be replaced.
Test Product, Dose, and Mode of Administration 
• 20 mg dose: Two IW-1973 Tablets, 10 mg administered orally• 40 mg dose: Two IW-1973 Tablets, 20 mg administered orally

Reference Therapy, Dosage, and Mode of Administration

Placebo to match IW-1973 Tablets: Two tablets administered orally

Study Periods

The study will consist of 3 periods (see [Study Schematic](#)).

Screening Period: The Screening Period will begin with the signature of the informed consent form (ICF) at the Screening Visit and may last up to 45 days. At the Screening Visit (which can occur from Day -45 to Day -15), patients will undergo preliminary screening procedures to determine their eligibility. Eligible patients will return to the clinic for the Baseline Visit (Day 7 ± 3) for baseline and eligibility assessments including 24-hour ambulatory blood pressure monitoring (ABPM). The end of the Screening Period will coincide with the beginning of the Treatment Period.

Treatment Period: The Treatment Period will begin on Day 1 at Randomization (there is no Day 0) and will end after the End of Treatment Visit on Day 87 (± 3). Patients will be stratified by baseline eGFR (ie, eGFR 30 to 45, >45 to 60, and >60 to 75 mL/min/1.73 m²) and randomized in a 1:1:1 ratio to receive 20 mg IW-1973, 40 mg IW-1973, or placebo for approximately 12 weeks.

Dosing on Days 1 to 7 (± 1) will be BID (twice daily), morning and evening; dosing on Day 8 (± 1) onward will be QD (once daily), 2 tablets in the morning.

[figure not shown]
At the Randomization Visit on Day 1, patients will receive their morning dose of study drug in the clinic and will undergo safety, efficacy, and pharmacokinetic (PK) assessments, including blood and urine collections at prespecified times ([Schedule of Events](#)). Patients must stay in the clinic at least 6 hours postdose and may leave the clinic at the Investigator's discretion following all study procedures.

At the Week 1 Visit on Day 8 (± 1), patients will return to the clinic and receive their first QD dose of study drug in the clinic. Patients will undergo safety, efficacy, and PK assessments, including blood and urine collections at prespecified times (see [Schedule of Events](#)). Patients must stay in the clinic at least 6 hours postdose and may leave the clinic at the Investigator's discretion following all study procedures.

At the Week 4 (Day 29 ± 3), Week 8 (Day 57 ± 3), and End of Treatment (Day 87 ± 3) Visits, patients will return to the clinic for study drug administration; safety, efficacy, and PK assessments; and study drug supply, if applicable (see [Schedule of Events](#)).

Follow-up Period: The Follow-up Period will begin immediately after the End of Treatment Visit and will last for 28 (± 3) days. At the Follow-up Visit on Day 115 (± 3), patients will return to the clinic for final study assessments (see [Schedule of Events](#)).

Study Schematic

Study Drug Administration

During Week 1, patients will take study drug BID ($2 \times$ /day), 1 tablet in the morning and 1 tablet approximately 12 hours later in the evening, preferably at approximately the same times each day. From the Week 1 Visit (Day 8 ± 1) on, patients will take study drug QD ($1 \times$ /day), 2 tablets in the morning, preferably at approximately the same time each day. Patients should take study drug with water, may take study drug with or without food, and, for QD dosing, may swallow tablets together, if desired. On study visit days, patients will receive their study drug dose in the clinic (on Randomization Day, patients will receive only their morning dose in the clinic). Study visits should be scheduled in the morning to accommodate regular dosing schedule.

Duration of Treatment

Patients will receive daily study drug for up to 90 days. Total patient participation will be 131 to 163 days, including the Screening, Treatment, and Follow-up Periods.

Dose Reduction

Per Investigator discretion, on a per-patient basis, dose may be reduced by half, ie, from 2 tablets daily to 1 tablet daily (in the morning). Each patient's dose may only be reduced once and may not be increased after reduction. Investigators should notify the Medical Monitor of all decisions to dose reduce on a per-patient basis.

Individual Stopping Criteria and Data Monitoring Committee Reviews

If any events included in the table below are reported during the study and are judged to be both study drug related and a serious adverse event (SAE; per causality and SAE definitions in the protocol), individual stopping criteria or Data Monitoring Committee (DMC) review will be triggered as described below. The inclusion of these AEs is based on the clinical experience with IW-1973, the prescribing information for riociguat, and the patient population for this study.

Treatment-emergent, Study Drug-related SAE Category	# of patients to trigger DMC review
Renal failure (eGFR <15 mL/min/1.73 m ² ; dialysis or renal transplant indicated)	2
Spontaneous bleeding events (eg, hemoptysis, subarachnoid or subdural hemorrhage, hematemesis, hematochezia)	2
Symptomatic hypotension-related events (eg, syncope)	2

DMC=Data Monitoring Committee; eGFR=estimated glomerular filtration rate; SAE=serious adverse event

Individual

On an individual basis, a patient will be discontinued from study drug dosing if 1 or more SAEs from the table is reported. At the Investigator's or Sponsor's discretion, any AE(s) of concern can likewise be the basis for patient discontinuation from the trial.

Study

An independent DMC will review trial safety data. The DMC will comprise experts in cardiovascular and/or renal disease and/or diabetes and a biostatistician who have experience in clinical trials and are not involved in the conduct of this trial.

Periodic safety review meetings will be scheduled after 30 subjects have been randomized or 5 months after the first subject is randomized (whichever is earlier) and when approximately 1/3 and 2/3 of patients have completed or discontinued treatment. The committee will review accumulated AE data and recommend trial continuation, continuation with modification, or termination. For these periodic reviews, the DMC will be provided with summaries of AE and blood pressure data. If a safety/tolerability signal or concerning AE imbalance is identified at a review, the committee can request unblinding of the masked treatment groups and may request additional safety data (eg, vital signs, concomitant medications).

The DMC will also be required to perform an ad hoc review if SAEs from the same category in the above table are reported at the incidence indicated in the table shown above (eg, 2 patients with spontaneous bleeding SAEs). In this circumstance, the DMC will be provided with narrative descriptions and all relevant clinical supporting documentation related to the SAEs. Upon request, the unblinded treatment codes and dose the subjects with the SAEs received will be made available to the committee.

In addition to the periodic and ad hoc reviews, during the trial, committee members will be provided with blinded reports on all SAEs. The DMC or the Sponsor may request ad hoc meetings at any time.

Final decision-making authority regarding study conduct will rest with the Sponsor. Additional details will be provided in the DMC charter, which will be developed in collaboration with the DMC members and will be finalized before the first patient is randomized.

Study Assessments

All study assessments will be performed according to the [Schedule of Events](#).

Clinical Laboratory Assessments

Complete blood count, serum chemistry panel, urinalysis, coagulation panel, UACR (urine albumin [mg/dL] / urine creatinine [g/dL]), estimated glomerular filtration rate (eGFR; by the Chronic Kidney Disease Epidemiology Collaboration [CKD-EPI] creatinine equation), hemoglobin A1c, Homeostatic Model Assessment to estimate insulin resistance (HOMA-IR), [REDACTED], urine pregnancy, and screens for hepatitis, human immunodeficiency virus, and drugs of abuse.

Hemodynamics and Vital Signs

Seated and standing BP (systolic and diastolic) and pulse measurements by automated office blood pressure (AOBP), ambulatory BP (systolic and diastolic) and pulse monitoring, respiratory rate, oral temperature. Orthostatic (standing minus seated) measurements will be calculated for BPs and pulse.

[REDACTED]

[REDACTED]

Other

Adverse-event recording, electrocardiograms (ECGs), physical examinations, concomitant medications.

Pharmacokinetics

Plasma IW-1973 concentrations will be measured.

[REDACTED]

[REDACTED]

[REDACTED]

[REDACTED]

[REDACTED]

[REDACTED]

[REDACTED]

[REDACTED]

Study Endpoints

Primary Endpoints

- Primary Safety: Incidence of TEAEs and study drug-related TEAEs
- Primary Efficacy: Change from baseline in UACR over Weeks 8 and 12

Statistical Methods

Sample Size Determination

Using an estimate of standard deviation of 0.67, a sample size of 40 patients per treatment group would provide approximately 80% power to detect a mean between-group difference of -0.376 units in change from baseline in log-transformed UACR over 12 weeks, with a one-sided significance level of 0.05 for at least 1 dose versus placebo comparison. This difference corresponds to a 31% between-group reduction of geometric mean change from baseline in UACR. Assuming a drop-out rate of 20%, approximately 150 patients will be randomly assigned in a 1:1:1 ratio (approximately 50 patients per treatment group) to 20 mg IW-1973, 40 mg IW-1973, or placebo.

Analysis Populations

Safety Population: The Safety Population will consist of all randomized patients who receive at least 1 dose of study drug. Patients in this population will be evaluated according to the treatment they actually received.

Intent-to-Treat (ITT) Population: The ITT Population will consist of all randomized patients who receive at least 1 dose of study drug. Patients in this population will be evaluated according to the treatment group they were assigned at Randomization.

PK Population: The PK Population will consist of all randomized patients who receive at least 1 dose of study drug and have at least 1 postdose PK parameter assessment.

Per-Protocol (PP) Population: The PP Population will consist of all ITT patients who did not have any major protocol deviations or dose reduction.

Efficacy Analyses

Corresponding with the primary efficacy objective of the trial, the primary inference for hypothesis testing is the treatment difference between the placebo group and the IW-1973 groups on the change from baseline in log UACR over Weeks 8 and 12. The primary efficacy analysis will be conducted using the ITT population using a mixed-effects model repeated measures (MMRM) analysis with change from baseline in log-transformed UACR as the response variable, treatment, site, visit, treatment-by-visit interaction, and baseline eGFR stratum as fixed effects, and baseline log UACR and baseline mean arterial pressure as covariates with unstructured as the variance-covariance structure. Treatment differences between the pooled IW-1973 dose groups and the placebo group will be estimated overall. The null hypothesis of the test will be interpreted as equality between the placebo and pooled treatment groups, and rejection of the null hypothesis as evidence that the pooled IW-1973 groups have a greater effect on lowering UACR than the placebo group. If the null hypothesis is rejected, the nature of these differences will be explored further by estimating the treatment differences between each IW-1973 dose group and the placebo group overall and at each assessment timepoint. Least square (LS) means, and LS mean differences between each

IW-1973 group and placebo, and their associated one-sided 95% confidence intervals will be calculated overall and for each assessment timepoint. The contrasts between each IW-1973 dose group and the placebo group at each assessment timepoint will be compared using a one-sided significance level of 0.05. If the treatment-by-visit interaction is significant at the 0.1 significance level, LS mean treatment differences relative to the previous visit will also be presented.

All change-from-baseline efficacy parameters will use the same MMRM model. Treatment group differences in the proportion of patients who achieved a 30% or 40% reduction in UACR from Baseline to Week 12 will be analyzed using Cochran-Mantel-Haenszel (CMH) test stratified by Baseline eGFR stratum.

Summary statistics will be presented by treatment group for the biomarker parameters. Change from Baseline in these variables will also be presented, where applicable.

Safety Analyses

Adverse events (AEs) will be summarized by treatment group with preferred term (PT) under system organ class (SOC). Listings will be provided for pretreatment AEs, treatment-emergent AEs (TEAEs), severe AEs, study drug-related AEs, SAEs, and AEs leading to study discontinuation. Descriptive statistics will be provided for all safety parameters (electrocardiogram [ECG], vital signs, and clinical laboratory tests).

ECGs, vital signs, [REDACTED] and clinical laboratory tests will be summarized at each timepoint and listings will be provided for patients with abnormal values.

PK

Summary statistics of IW-1973 plasma concentrations will be presented.

[REDACTED]

Interim Analysis

After at least one half of the subjects ($N \geq 75$) have completed the last visit, an interim analysis of unblinded efficacy data may be performed to assist with the planning of future studies. If performed, details regarding the interim analyses will be included in the SAP, along with updates to the data management plan as necessary. The independent statistician (who will not be involved in study data collection or interpretation) performing the interim analysis and Ironwood staff members, as identified in the SAP, may be unblinded. DMC reviews of safety data will be independent of this possible interim analysis of efficacy.

Final Date: 20 December 2017

TABLE OF CONTENTS

STUDY IDENTIFICATION	2
SYNOPSIS.....	3
LIST OF ABBREVIATIONS AND DEFINITIONS OF TERMS.....	17
ELIGIBILITY CRITERIA.....	21
INCLUSION CRITERIA.....	21
EXCLUSION CRITERIA	22
SCHEDULE OF EVENTS	25
1. INTRODUCTION	28
1.1 DIABETIC NEPHROPATHY.....	28
1.2 THE NO-SGC-CGMP PATHWAY	29
1.3 RATIONALE FOR USE OF AN SGC STIMULATOR IN DIABETIC NEPHROPATHY	30
1.4 IW-1973 BACKGROUND.....	30
1.4.1 Nonclinical Studies in Support of DN	30
2. STUDY OBJECTIVES.....	32
3. INVESTIGATIONAL PLAN.....	33
3.1 OVERALL STUDY DESIGN AND PLAN.....	33
3.2 DISCUSSION OF STUDY DESIGN AND CONTROL GROUP.....	35
3.3 STUDY DURATION	35
3.4 STUDY POPULATION	35
3.4.1 Study Population Description	35
3.4.2 Removal of Patients from Therapy or Assessment.....	36
3.4.3 Early Termination Procedures	37
3.4.4 Replacement Procedures	37
3.5 STUDY TREATMENT(S).....	37
3.5.1 Description of Treatment(s).....	37
3.5.1.1 Investigational Product	37
3.5.1.2 Placebo.....	37

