3.8.8.3 Urine Albumin Creatinine Ratio (UACR)

UACR will be calculated as urine albumin (mg/dL) / urine creatinine (g/dL).

Urine albumin and urine creatinine levels will be determined as part of the clinical laboratory tests ([Table 4](#)). At the Screening Visit, a single urine sample, which may not be first void, will be collected for determination of albumin and creatinine levels. For subsequent study visits, patients will be given urine collection supplies and will collect 2 first-void urine samples on the 2 consecutive mornings before each scheduled visit.

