4.1.2 Primary Efficacy

- Change from baseline in UACR over Weeks 8 and 12

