5.2 DETERMINATION OF SAMPLE SIZE

Using an estimate of standard deviation of 0.67, (29) a sample size of 40 patients per treatment group would provide approximately 80% power to detect a mean between-group difference of -0.376 units in change from baseline in log-transformed UACR over 12 weeks, with a one-sided significance level of 0.05 for at least 1 dose versus placebo comparison. This difference corresponds to a 31% between-group reduction of geometric mean change from baseline in UACR. Assuming a drop-out rate of 20%, approximately 150 patients will be randomly assigned in a 1:1:1 ratio (approximately 50 patients per treatment group) to 20 mg IW-1973, 40 mg IW-1973, or placebo.

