5.9 EFFICACY ANALYSES

All efficacy analyses will be based on the ITT and PP Populations.

Corresponding with the primary efficacy objective of the trial, the primary inference for hypothesis testing is the treatment difference between the placebo group and the IW-1973 groups on the change from baseline in log UACR over Weeks 8 and 12. The primary efficacy analysis will be conducted using the ITT population using a mixed-effects model repeated measures (MMRM) analysis with change from baseline in log-transformed UACR as the response variable, treatment, site, visit, treatment-by-visit interaction, and baseline eGFR stratum as fixed effects, and baseline log UACR and baseline MAP as covariates with unstructured as the variance-covariance structure. Treatment differences between the pooled IW-1973 dose groups and the placebo group will be estimated overall. The null hypothesis of the test will be interpreted as equality between the placebo and pooled treatment groups, and rejection of the null hypothesis as evidence that the pooled IW-1973 groups have a greater effect on lowering UACR than the placebo group. If the null hypothesis is rejected, the nature of these differences

will be explored further by estimating the treatment differences between each IW-1973 dose group and the placebo group overall and at each assessment timepoint. Least square (LS) means, and LS mean differences between each IW-1973 group and placebo, and their associated one-sided 95% confidence intervals will be calculated overall and for each assessment timepoint. The contrasts between each IW-1973 dose group and the placebo group at each assessment timepoint will be compared using a one-sided significance level of 0.05. If the treatment-by-visit interaction is significant at the 0.1 significance level, LS mean treatment differences relative to the previous visit will also be presented.

All change-from-baseline efficacy parameters will use the same MMRM model.

Treatment group differences in the proportion of patients who achieved a 30% or 40% reduction in UACR from baseline to Week 12 will be analyzed using Cochran-Mantel-Haenszel (CMH) test stratified by baseline eGFR stratum.

Summary statistics will be presented by treatment group for the biomarker parameters. Change from baseline in these variables will also be presented, where applicable.

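### The primary MMRM imposes one baseline log UACR slope on all modelled visits, which may cost some precision in the Week 8/12 contrast; a baseline-by-visit term would avoid this almost for free

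*Protocol*

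**What the plan says.** The synopsis (Statistical Methods, Efficacy Analyses) and Section 5.9 give the same primary model. The outcome is "change from baseline in log-transformed UACR as the response variable". The synopsis lists the terms as "treatment, site, visit, treatment-by-visit interaction, and baseline eGFR stratum as fixed effects, and baseline log UACR and baseline mean arterial pressure as covariates". Visit interacts with treatment and with nothing else. Section 5.9 ends the list with "and baseline log UACR and baseline MAP as covariates with unstructured as the variance-covariance structure", so baseline enters once and has no visit interaction.

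The primary efficacy endpoint in Section 4.1.2 is "Change from baseline in UACR over Weeks 8 and 12". The primary test compares both doses together with placebo: "Treatment differences between the pooled IW-1973 dose groups and the placebo group will be estimated overall".

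The protocol does not list the visits in the model. After Screening, patients "will collect 2 first-void urine samples on the 2 consecutive mornings before each scheduled visit" (Section 3.8.8.3), so UACR exists at Weeks 1 and 4 as well as at Week 8 and End of Treatment. Section 5.9 also plans dose-versus-placebo contrasts at every assessment timepoint and, if the treatment-by-visit interaction is significant, differences relative to the preceding visit. Section 5.1 leaves further statistical detail to an SAP that is to be finalized before unblinding.

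**The concern.** When the response is change from baseline, its slope on baseline at a visit is roughly the correlation with baseline minus one, if variances are similar across visits. If that correlation falls between Week 1 and Week 12, the slope steepens over the same period. A model with one slope must compromise. Under an unstructured covariance the compromise is weighted by precision, and it favours the early visits, where change has the smallest residual variance. Weeks 8 and 12, the only visits in the primary endpoint, would then be adjusted with a slope that is too shallow, and baseline variance that the model could have removed would stay in the contrast.

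What is at stake is the precision of the primary estimate, in a trial planned on 40 evaluable patients per arm.

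**Working it through.** **1. The plan's own figures.** Section 5.2 gives SD 0.67, difference 0.376, one-sided 0.05 and 40 per arm. By the normal approximation, 0.376 / (0.67 × √(2/40)) = 2.51, and Φ(2.51 − 1.645) = 80.6% (80.0% with the t distribution). Allowing for dropout, 40 / 0.80 = 50 per arm, or 150 in total. The effect is 1 − exp(−0.376) = 31%. All of these reproduce. For the pooled primary contrast (80 vs 40) at the same inputs, 0.376 / (0.67 × √(1/80 + 1/40)) = 2.90, which gives 89.5%.

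**2. Inputs that the protocol does not give (assumptions).** The model holds Weeks 1, 4, 8 and 12. Log UACR variance is equal at each visit and is set to 1, so the slope is ρ − 1 and the residual variance is 1 − ρ², where ρ is the correlation with baseline. The residual correlation between visits, r, is 0.3 to 0.7.

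**3. Formula.** With complete data, the common-slope model adds (late slope − common slope)² to the residual variance of the Week 8/12 average. The common slope is the generalized least squares weighted mean of the four visit slopes.

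**4. Worked case: moderate decay, r = 0.5.**
- ρ = 0.90, 0.82, 0.72, 0.68, so the slopes are −0.10, −0.18, −0.28, −0.32 and the late average is −0.30.
- Residual variances are 0.190, 0.328, 0.482, 0.538.
- The weights are about 0.737, 0.229, 0.036 and −0.003, so the common slope is about −0.124. Week 1 alone carries nearly three quarters of the weight.
- Residual variance of the Week 8/12 average: (0.482 + 0.538 + 2 × 0.5 × √(0.482 × 0.538)) / 4 = 0.382.
- Added variance: (0.300 − 0.124)² = 0.031. The ratio is 0.413 / 0.382 = 1.081, so the SE is 4.0% larger.

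**5. Range over r = 0.3 to 0.7.**

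| Correlation with baseline, Weeks 1/4/8/12 | SE increase without the interaction |
|---|---|
| Equal, 0.75 throughout | 0% |
| Mild, 0.82/0.78/0.74/0.72 | 0.3 to 0.6% |
| Moderate, 0.90/0.82/0.72/0.68 | 3 to 6% |
| Steep, 0.93/0.82/0.66/0.58 | 9 to 14% |
| Extreme, 0.97/0.85/0.60/0.50 | 18 to 20% |

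**6. If only Weeks 8 and 12 are modelled.** In the moderate case the two slopes are −0.28 and −0.32. Their common slope must lie close to −0.30, so the loss is negligible.

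**7. What the loss is measured against.** In the worked case the Week 8/12 average has variance 0.382 + 0.300² = 0.472 with no baseline adjustment, 0.413 with the common slope and 0.382 with visit-specific slopes. The protocol's model keeps (0.472 − 0.413) / 0.090 = 66% of the available gain. Over r = 0.3 to 0.7 in the moderate case it keeps about 77% to 40%.

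**8. Simulation check.** An unstructured ML MMRM was simulated with 50 per arm, four visits, 20% monotone dropout, r = 0.5 and 600 runs per scenario, leaving out site, eGFR stratum and MAP. The SE ratios without versus with the interaction were 1.00 (equal), 1.00 (mild), 1.04 (moderate) and 1.12 (steep). Mean estimates agreed within 0.001. Rejection under the null was 0.053 without the term and 0.057 with it; the Monte Carlo error is √(0.05 × 0.95 / 600) = 0.009.

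**The case against.** The strongest reply is that this is a preference and not an error. The stated model is valid, adjusts for baseline log UACR already, reads the same in both places and contradicts nothing else in the protocol. The modelled visits are not named; Weeks 8 and 12 are themselves assessment timepoints, so a two-visit model fits the text and step 6 then leaves nothing to recover. The correlations are assumed, and with equal slopes the loss is zero. All of this stands. It makes the point conditional and low in severity. It does not remove it, because the protocol fixes the term list itself, and four-visit modelling is the more natural reading of contrasts by timepoint and differences from the preceding visit.

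A reader might also infer more than the documents support:

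- **That power falls below 80%.** Multiplying 0.67 by the moderate SE increase gives 76.5 to 78.5% for one dose. But the increase compares two baseline-adjusted models. Section 5.2 says only "Using an estimate of standard deviation of 0.67" and mentions no baseline adjustment, so 0.67 is taken here as the SD before adjustment. Under mild and moderate decay the common-slope model still has a smaller variance than no adjustment at all (step 7). The primary test also pools the doses: even with that scaling its power is about 86 to 88%.
- **That chance baseline imbalance or dropout biases the result.** Leftover imbalance averages to zero under randomization and is the same loss of precision counted again. The simulation with dropout showed no bias.

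**Conclusion.** The point holds as a conditional, low-severity matter of efficiency. One baseline slope is imposed on all modelled visits. If Weeks 1 and 4 are modelled and the correlation with baseline decays, the early visits dominate that slope and the primary contrast is under-adjusted. The likely size runs from nothing to a few percent of the SE: 0% with equal slopes, under 1% with mild decay, about 3 to 6% with moderate decay. Losses of 9% or more need a steep fall in correlation, and no figure in the protocol shows that this applies.

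Validity is not in question, the sample-size figures reproduce, and a shortfall against the stated power is not shown. The conclusion rests on the assumed correlations, equal variances across visits and a four-visit model.

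**What to change.** In Section 5.9 and the matching synopsis paragraph, add a baseline log UACR-by-visit interaction to the primary MMRM and name the visits in the model. All other terms stay as they are. With four visits this uses about three degrees of freedom (4 − 1) and needs no new data, visits or patients. In the simulation it carried no visible SE penalty when slopes were equal (ratio 1.00). Make the change before unblinding, so that the choice cannot depend on the results, and carry the same wording into the SAP.
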